5. GENERAL STATISTICAL METHODS

5.1. Sample Size Justification

The sample size of the study was determined based on the precision of the estimate of the treatment effect for the primary endpoint – the percent change from baseline in urine protein/creatinine ratio [UPCR(mg/mg)] as measured in 24-hour urine at Week 32. It should be noted that geometric mean ratio of UPCR at Week 32 to baseline is statistically equivalent to mean of the change from baseline in logarithm of UPCR. Therefore, the effect size of the study is defined as the difference of change from baseline between cemdisiran and placebo in the logarithm of UPCR.

Based on the NEFIGAN study, [Fellstrom 2017] we assume that in the placebo arm the geometric mean ratio of UPCR at Week 32 to baseline is 0.88 (log standard deviation [SD] 0.597), corresponding to a 12% reduction, while the geometric mean ratio is 0.5, or a 50% reduction for the cemdisiran arm. Using these assumptions, sample size of 9 and 18 in the placebo and cemdisiran arms will provide a width of 0.80 (+/- 0.4) for the 90% confidence interval (CI) for treatment effect size estimate (cemdisiran – placebo) in log scale.

5.2. General Methods

Categorical variables will be summarized by frequency and percentage in each category. Continuous variables will be summarized by the number of patients, mean, median, standard deviation (SD), interquartile range (Q1, Q3), minimum, maximum and geometric mean (GM) when appropriate. For log-transformed data, coefficient of variation (CV) and geometric mean (GM) will also be presented. CV is calculated as

 $\sqrt{\exp(\text{variance of log transformed data)} - 1 \times 100\%}$.

For the summary statistics of all numerical variables unless otherwise specified, minimum and maximum will be displayed to the same level of precision as reported. Median, mean, standard deviation and standard error will be presented to the level of precision collected in database plus one additional decimal.

Day 1 will be defined as the day of the first dose of study drug (cemdisiran or placebo). Study Day is relative to first dosing date of study drug for all patients.

• If the assessment date is after the date of first study drug dose, then the study day will be calculated as:

Study Day = Date of assessment - date of first dose of study drug + 1

• If assessment date is before the date of the first dose of study drug, then study day will be calculated as:

Study Day = Date of assessment – date of first dose of study drug

For patients who were randomized to placebo and switched to cemdisiran in OLE period, an additional study day will be defined which reflects the study days relative to the first dose of cemdisiran.

For laboratory parameters, any assessments recorded as lower than the lower limit of quantification (LLOQ) will be replaced by the respective LLOQ value. Any assessment recorded as greater than the upper limit of quantification (ULOQ) will be replaced by the respective ULOQ value. For assessments with repeated collections at a given study visit (e.g. ECG parameters) the mean will be used as the value at the visit for all parameters.

For all analysis sets except for the All Cemdisiran Treated Set, summaries will be presented by treatment arm (cemdisiran and placebo). For the All Cemdisiran Treated Set, summaries will be presented by the following treatment sequence groups:

- Cemdisiran / Cemdisiran: all patients who received cemdisiran during the DB period, including patients who continued to receive cemdisiran during the OLE period and patients who discontinued treatment during the DB period
- Placebo / Cemdisiran: all patients who received placebo during the DB period and switched to cemdisiran in the OLE period
- All Cemdisiran: all patients who received at least one dose of cemdisiran during either the DB or OLE period

5.3. Baseline Definitions

Baseline value for 24-hour UP, UPCR, and UACR will be calculated as the average of two valid (as per section 6.4.1.1 of the protocol) collections at week -2 visit (i.e., the last measurement prior to the first dose of study drug). Baseline values for vital signs will be defined as the assessments at week -2 visit because of the required vaccination when applicable. The baseline value for an ECG variable (heart rate, PR interval, QRS interval, QT interval or QT_c interval) will be the average of last triple assessments prior to the first dose of study drug (Day 1). For other parameters, baseline is defined as the last non-missing value prior to the first dose date/time of the study drug, unless otherwise specified.

For the All Cemdisiran Treated Set, baseline for patients randomized to cemdisiran in DB period is as defined above. For patients who switched from placebo in the DB period and received at least one dose of cemdisiran in the OLE period, baseline for all parameters will be redefined as the last non-missing assessments prior to the first dose of cemdisiran, except for assessments based on 24-hour urine collections where the average of the two valid collections at week 32 visit will be the baseline value and for ECG variables where the average of the last triplet assessments prior to the first dose of study drug in OLE period will be the baseline.

5.4. Randomization Stratification Factors

The randomization will be stratified based on the baseline 24-hour UP ($\geq 1g/24$ -hour and <2g/24-hour versus $\geq 2g/24$ -hour). The mean of two valid 24-hour urine protein assessments at week -2 visit will be used to determine the stratification. The stratification factor will be recorded in both the IRS and the clinical database.

5.5. Multiple Comparisons/Multiplicity

All comparisons will be descriptive in nature and no multiplicity adjustment will be made.

5.6. Missing Data

Missing values will not be imputed, unless otherwise specified.

Patients who discontinue the study prior to Week 36 visit will be encouraged to remain on study and complete their remaining clinical visits (excluding PK assessments) through the visit at Week 36. All data collected regardless of whether it was collected before or after treatment discontinuation will be used for analysis. However, it is possible that data will remain missing.

In case of missing date or partial date of adverse event (AE) onset, an AE will be considered treatment-emergent unless it can be unequivocally determined (from the partial onset date and/or a partial or complete stop date) that the event occurred prior to first dose of study drug.

For medications with partial start or stop dates: the first day/month will be imputed for start date, and the last day/month will be imputed for stop date. For medications with a completely missing start date, the medications will be considered as started prior to the first dose of study drug in this study; medications will be classified as prior or both prior and concomitant depending on the medication stop dates. If any medications have a completely missing stop date, then the medication will be assumed as ongoing.

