5.10. Primary and Final Analyses

The study includes a 36-week DB period, a 156-week OLE period, and a 52-week safety follow up period. The primary analysis is to evaluate the efficacy and safety of cemdisiran compared to placebo during the DB period.

For the primary analysis, tables and figures will be presented by treatment arm (cemdisiran, placebo). Selected outputs will also be summarized by treatment sequence (cemdisiran/cemdisiran, placebo/cemdisiran and all cemdisiran treated). When assessments or AE onset dates are exactly the first dose date in the OLE period with time missing, the records will be included in the OLE period. Per-patient listings will include all data collected during the entire study. The listings will be sorted by randomized arm. Within patient, there will be a variable to indicate the period of the data collection.

Final analysis evaluating the long-term efficacy and safety of cemdisiran will be described for the All Cemdisiran Treated Set. Summary tables and figures will be presented by treatment sequence (cemdisiran/cemdisiran, placebo/cemdisiran and all cemdisiran treated).

For patients who received placebo in the DB period and switched to cemdisiran in the OLE period, the intra-patient comparison of the two treatment periods will be conducted for 24-hour UP, 24-hour UPCR, spot UPCR and eGFR in the final analysis. The time period during which patients receiving cemdisiran (i.e. on or after the first date/time of cemdisiran) is referred as "during cemdisiran treatment".

The detailed definitions for different study periods are as the following:

• DB Period

It is defined as the time between the first dose of study drug and Week 36/end of study (EOS) visit. For patients who do not have the Week 36/EOS visit, it is the time between the first dose of study drug and the targeted Week 36/EOS visit (Day 252).

• OLE Period

The start date of the OLE period is defined as the first dose of cemdisiran of the OLE period (i.e., week 36 visit) and ends at week 188/EOS visit.

• Safety Follow-up Period

The 52-week safety follow-up period starts at week 36/EOS visit (for patients not continuing into the OLE) or week 188/EOS visit.

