7.6. Safety Analyses

Primary safety analyses will compare cemdisiran versus placebo during the DB period using the Safety Analysis Set. Long-term safety analyses of cemdisiran will be summarized by treatment sequence (cemdisiran/cemdisiran, placebo/cemdisiran, all cemdisiran treated arm) using the all Cemdisiran Treated Analysis set.

The primary safety parameter is the frequency of treatment emergent adverse events (TEAEs). A TEAE is defined as an AE that occurred or worsened on or after the first dose of study drug through 28 days after the last dose of study drug. In addition, an AE that occurs after the 28 days from the last dose but is considered to be related to study drug, is considered to be a TEAE. Other safety parameters include vital signs, ECGs, clinical laboratory assessments, and physical exams. Adverse events that are non-treatment emergent (e.g., during safety follow up period) will be summarized and listed separately.

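### The rule for incomplete AE onset dates (SAP 5.6) omits the upper limit of the TEAE definition (SAP 7.6), so the two sections classify some late, unrelated events differently

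*SAP*

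**What the plan says.** SAP Section 5.6 sets the default for an incomplete onset date: "an AE will be considered treatment-emergent unless it can be unequivocally determined (from the partial onset date and/or a partial or complete stop date") to have begun too early. The stated test is "that the event occurred prior to first dose of study drug", and it is the only way out of treatment-emergent status.

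SAP Section 7.6 defines the window with two limits: an "AE that occurred or worsened on or after the first dose of study drug through 28 days after the last dose of study drug". It then makes one extension: "an AE that occurs after the 28 days from the last dose but is considered to be related to study drug, is considered to be" treatment-emergent. It also says what happens to the rest: "Adverse events that are non-treatment emergent (e.g., during safety follow up period) will be summarized and listed separately".

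SAP Section 5.10 fixes the off-drug period: "The 52-week safety follow-up period starts at week 36/EOS visit (for patients not continuing into the OLE) or week 188/EOS visit". Section 7.6.1 uses the term AE for TEAEs from that point on, so every AE table inherits the flag.

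Nothing in the current SAP limits the 5.6 rule or says that 7.6 takes precedence. The 5.6 rule has the same content in the two superseded SAP versions reproduced in the same file, so it is not an amendment slip.

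**The concern.** Treating an event as emergent when its date cannot be resolved is a sound, cautious convention. Here, however, the default also applies when the partial date does resolve the question. A month and year can prove that onset came more than 28 days after the last dose, yet 5.6 gives that proof no effect. An unrelated event with a full date in the same month is not a TEAE. Classification then depends on how completely the date was recorded, not on when the event happened.

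TEAE frequency is the primary safety parameter (Section 7.6), and AE frequency is a listed secondary endpoint (Section 3, Table 1). Misplaced events would enter the overview, severity, SAE and SOC/PT tables and drop out of the separate non-treatment-emergent summary. Section 7.6.1 also plans exposure-adjusted rates, while Section 6.4 ends exposure no later than 28 days after the last dose. If that exposure is the denominator, such an event adds to the numerator without matching person-time.

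**Working it through.** **Step 1: the two rules side by side, for an AE not related to study drug**

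| Onset information | Section 5.6 | Section 7.6 |
|---|---|---|
| Full date, more than 28 days after last dose | rule not engaged | not TEAE |
| Month and year, month wholly before first dose | not TEAE | not TEAE |
| Month and year, month wholly after last dose + 28 days | TEAE | not TEAE |
| Month and year, month containing the end of the window | TEAE | cannot be decided |
| Date completely missing | TEAE | cannot be decided |

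Only the third row is a contradiction. In the last two rows the default does its proper work. Events judged related to study drug are TEAEs after the first dose under both sections.

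**Step 2: how much of follow-up lies outside the window**

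Inputs: end of treatment at Weeks 32 and 184 and end of study at Weeks 36 and 188 (Figure 1, with the end-of-treatment visit taken as the scheduled last dose); 28-day limit (Section 7.6); 52-week follow-up (Section 5.10).

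- No OLE: 32 + 28/7 = Week 36; follow-up runs from Week 36 to 36 + 52 = 88.
- With OLE: 184 + 28/7 = Week 188; follow-up runs from Week 188 to 188 + 52 = 240.

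On schedule the window closes where follow-up opens, so essentially all 52 weeks lie outside it.

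**Step 3: can a month and year prove late onset?**

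Take an illustrative first dose on 15 January 2020 (an assumption; the logic does not depend on it). The Week 184 dose falls on 26 July 2023, the window ends on 23 August 2023 and follow-up ends on 21 August 2024. Of the 13 calendar months touching follow-up, 12 lie wholly after the window. An unrelated AE recorded as March 2024, day missing, began on 1 March 2024 at the earliest. That is 219 days after the last dose, or 219 − 28 = 191 days past the limit. Section 5.6 makes it a TEAE; Section 7.6 does not.

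**Step 4: size**

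The SAP gives neither the share of incomplete onset dates nor an off-drug AE rate, so the effect cannot be computed. For a range, assume a share p of incomplete dates, a constant AE rate on and off drug, full follow-up for every patient, all follow-up AEs unrelated, and every incomplete date decisive. Then:

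inflation of the TEAE count = p × 52 / (weeks in the TEAE window)

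The window is 188 weeks for cemdisiran/cemdisiran and 188 − 36 = 152 weeks for placebo/cemdisiran.

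| p (assumed) | p × 52/188 | p × 52/152 |
|---|---|---|
| 5% | 1.4% | 1.7% |
| 10% | 2.8% | 3.4% |

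These are upper bounds for patients on schedule. Related events, completely missing dates and straddling months all reduce the number that truly conflicts with 7.6.

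**The case against.** The strongest reply is that Section 7.6 already shows the intent. It closes the window, names follow-up events as its example of non-treatment-emergent AEs, and leaves 5.6 to be read as a fallback for dates that cannot be resolved. A programmer could apply 7.6 directly when the month settles the matter. That reading is sensible, but the wording of 5.6 does not require it, and two programmers could derive different flags from the same record.

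The reply on weight largely stands. The error overstates events on drug and hides none. AE tables carry no tests (Section 7.6.1), comparisons are descriptive (Section 5.5), and by-subject listings allow a misplaced event to be traced. About 30 patients are planned, so few events, if any, may be affected.

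Two stronger readings are tempting and are not supported:

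- A reader might set 52 follow-up weeks against the 36 double-blind weeks and infer a large distortion of the randomized comparison. No planned table works that way. The double-blind safety comparison ends at the Week 36/EOS visit, or Day 252 without that visit (Section 5.10), which is where follow-up starts. The long-term tables use only the treatment-sequence groups, and placebo patients who never enter the OLE are not in the All Cemdisiran Treated Set (Section 4.1). A cemdisiran patient who skips the OLE is one member of the cemdisiran/cemdisiran group.
- A reader might infer that every incomplete follow-up date is misclassified. Only those whose date parts prove late onset conflict with 7.6.

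**Conclusion.** The contradiction is in the text and needs no assumption: for an unrelated AE whose partial date proves onset more than 28 days after the last dose, Sections 5.6 and 7.6 give opposite answers. Its practical weight is modest. It falls mainly on the long-term All Cemdisiran Treated TEAE tables, the exposure-adjusted rates and the separate non-treatment-emergent summary. In the double-blind comparison it can matter only for patients who stop dosing early and remain in that period, as Section 5.6 encourages them to do. Efficacy is untouched.

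The percentages above show scale and are not estimates. They rest on an assumed p and on the conditions listed with them. A higher AE rate off drug, or shorter treatment in some patients, would raise them; the other simplifications push the true figure down. The point is worth correcting because the rule as written gives a wrong result and is easily repaired. It gives no reason to doubt the safety conclusions as a whole.

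**What to change.** Extend the sentence in SAP Section 5.6 to read, in substance: *an AE with a missing or partial onset date is considered treatment-emergent unless the available date parts show unequivocally that onset was before the first dose of study drug, or was more than 28 days after the last dose and the event is not considered related to study drug.*

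Keep the treatment-emergent default for completely missing dates and for months that straddle the end of the window.

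The cost is one clause in the SAP and one extra condition in the TEAE derivation. No new data are needed. The March 2024 example then becomes non-treatment-emergent under both sections.

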5.7. Visit Windows

For table and figure summaries of the DB period, all data will be tabulated and analyzed per the evaluation visit as recorded on the electronic case report forms (eCRF) even if the assessment is outside of window.

For table and figure summaries during cemdisiran treatment period, the data collected at study visits during the OLE period will be re-mapped for the patients randomized to placebo in the DB period to reflect the visit relative to the first dose of cemdisiran. Unless otherwise specified, data collected at an unscheduled visit will be included in by patient listings and/or spaghetti plot figures, but no assignment of the scheduled visit will be made for the purposes of summary tabulations. However, unscheduled study visits will be used in categorical shift tables (e.g. shift from baseline to worst post-baseline value).

5.8. Analysis Cutoff and Database Lock

As this study will be ongoing when the database lock for the primary analysis is performed, the study database will have an interim database lock (i.e. data in EDC will be frozen and external data such as laboratory data will be QA'd and cleaned), when the last patient completes Week 36 assessments. The study will then be unblinded and all data entered as of the date cutoff for the primary interim database lock will be included in the primary analysis. Additional details regarding the database lock are located in the study Data Management Plan.

After the study is completed, i.e., all patients complete the OLE period and the safety follow-up visits, a final database lock will occur, and all data collected will be summarized in the final CSR.

5.9. Interim Analyses

No formal interim analysis is planned for this study. Informal data looks prior to the primary interim analysis are planned for the monitoring of the study by DMC and the sponsor.

5.10. Primary and Final Analyses

The study includes a 36-week DB period, a 156-week OLE period, and a 52-week safety follow up period. The primary analysis is to evaluate the efficacy and safety of cemdisiran compared to placebo during the DB period.

For the primary analysis, tables and figures will be presented by treatment arm (cemdisiran, placebo). Selected outputs will also be summarized by treatment sequence (cemdisiran/cemdisiran, placebo/cemdisiran and all cemdisiran treated). When assessments or AE onset dates are exactly the first dose date in the OLE period with time missing, the records will be included in the OLE period. Per-patient listings will include all data collected during the entire study. The listings will be sorted by randomized arm. Within patient, there will be a variable to indicate the period of the data collection.

Final analysis evaluating the long-term efficacy and safety of cemdisiran will be described for the All Cemdisiran Treated Set. Summary tables and figures will be presented by treatment sequence (cemdisiran/cemdisiran, placebo/cemdisiran and all cemdisiran treated).

For patients who received placebo in the DB period and switched to cemdisiran in the OLE period, the intra-patient comparison of the two treatment periods will be conducted for 24-hour UP, 24-hour UPCR, spot UPCR and eGFR in the final analysis. The time period during which patients receiving cemdisiran (i.e. on or after the first date/time of cemdisiran) is referred as "during cemdisiran treatment".

The detailed definitions for different study periods are as the following:

• DB Period

It is defined as the time between the first dose of study drug and Week 36/end of study (EOS) visit. For patients who do not have the Week 36/EOS visit, it is the time between the first dose of study drug and the targeted Week 36/EOS visit (Day 252).

• OLE Period

The start date of the OLE period is defined as the first dose of cemdisiran of the OLE period (i.e., week 36 visit) and ends at week 188/EOS visit.

• Safety Follow-up Period

The 52-week safety follow-up period starts at week 36/EOS visit (for patients not continuing into the OLE) or week 188/EOS visit.

6. STUDY ANALYSES

6.1. **Patient Disposition**

Number and percentage of patients in the following categories will be summarized by treatment arm (or by treatment sequence) and overall, as appropriate:

- Screen failures (overall only)
- Enrolled for Run-in Period (signed informed consent and met eligibility criteria; overall only) and those failed during Run-in period
- Randomized
- Treated
- Modified Intent-to-Treat Analysis Set (mITT)
- Safety Analysis Set
- PK Analysis Set
- PD Analysis Set
- All Cemdisiran Treated Set (by treatment sequence)
- Entered the OLE period.

In addition, summaries of the number and percentage of patients who discontinued treatment, withdrew from study, and primary reasons for either discontinuation of treatment and/or withdrawal from study will be presented. The number and percentage of patients in each level of

randomization stratification factor, baseline 24-hour UP (>=1g/24-hours and <2 g/24-hours vs. ≥ 2 g/24-hours), recorded in IRS and the clinical database will be summarized by randomized treatment arm and overall. The numbers of subjects screened will be summarized by country and site.

Data listings of those patients who withdrew study and/or discontinued treatment including the associated reasons will also be presented. A separate listing of screening failure patients with the associated reason for screen failures will be generated.

